Participants will participate across 14 weeks. Those in Intervention first (Group A) will participate in three caregiver meetings held every two weeks across six weeks. This will be followed by data collection check-ins over 8 weeks. The second group (Group B) will begin with 8 weeks of data collection check-ins, followed by three caregiver meetings over 6 weeks. Each meeting will be scheduled every two weeks and last 60 minutes. Survey check-ins will be repeated six times

Protocol: EnACT RCT

Version: 7/20/2025

and will include completion of a survey via phone or internet. Two weeks after the final intervention meeting, participants will be invited to meet together to discuss thoughts about the caregiver training activities.

Frequency and duration of intervention. EnACT will be offered three times to each person. It will occur every two weeks for a total of three 60-minute sessions. Each participant will be invited to complete one take-home written exercise after session 1 and session 2, which will involve journaling about topics related to the session.

Study assessments for caregivers will include (total time = 95 minutes):

Baseline survey: 20 minutes

Time 2 survey: 15 minutes

Time 3 survey: 15 minutes

Time 4 survey: 15 minutes

Time 5 survey: 15 minutes

Time 6 survey: 15 minutes

Additional time commitments will include:

Study Eligibility Interview: 15 minutes

Final debrief focus group: 60-90 minutes

Reimbursement

Caregivers will receive \$25.00 for each caregiver meeting that they attend, \$10 for the completion of three surveys gathered outside of meetings, and \$50 to attend the final focus group meeting. It is possible to receive \$155.00 total in compensation. Payment will be distributed at the end of the study either through direct deposit or check. You will only be paid for each visit or survey that you complete. If you discontinue early from the study, you will receive a partial amount based on how many meetings and surveys you complete.

Assessment Schedule

Survey data will be gathered at six time points no less than two weeks apart over the course of control, intervention, and follow up.

Focus group data will be gathered during the debrief meeting two weeks after intervention meetings are complete.

Feasibility and Acceptability data will be gathered throughout. Satisfaction surveys will be gathered at the end of each intervention session as part of the session.

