Baseline Assessment (T1): Demographics, Imagined Interactions, Capacity to Adapt, Caregiver Capacity to Appraise Demands, Perceived Stress, Caregiver Well-being

Survey Assessment (Week 2 (T2), Week 5 (T3), Week 8 (T4), Week 11 (T5), Week 14 (T6): Imagined Interactions, Capacity to Adapt, Caregiver Capacity to Appraise Demands, Perceived Stress, Caregiver Well-being

Measures

Feasibility: number screened and enrolled, retention rates, levels of engagement, intervention delivery, assessment-protocol duration, and completion rates

Acceptability: satisfaction with intervention, audio/video documentation of intervention meetings, post-intervention focus groups

Focus Groups: questions on suggestions for improvement, preference compared to other programs they've experienced, barriers to or benefits of use.

Demographics: age, education, gender identity/sexual orientation, race/ethnicity, employment, salary, caregiving experience, frequency of theatre attendance, care-recipient relationship, caregiver support, time as caregiver, type of caregiver, sex and age of care partner, participation in caregiver training or support, type of caregiver training/support, frequency of caregiver training/support, activity/hobbies and frequency of participation.

Imagined Interactions: *Survey of Imagined Interactions* (7-point Likert scale questions) measures outcomes of imagining interactions, including four subscales: *Specificity* (5 items), *Discrepancy* (7 items), *Proactivity* (3 items)

Capacity to Adapt: *Resilience Scale* (7-point Likert scale questions) measures one's ability to adapt, specific to constructs of meaning, self-confidence, perseverance, serenity, and loneliness (25 items)

Caregiver Capacity to Appraise Demands: *Revised Caregiving Appraisal Scale* (RCAS; 5-point Likert scale questions) asks ADRD caregivers to assess the following five subscales: *Burden* (9 items), *Satisfaction* (6 items), *Mastery* (4 items), *Demand* (3 items), *Impact* (3 items)

Perceived Stress: *Perceived Stress Scale* (5-point Likert scale questions) measures self-reported stress (10 items)

Caregiver Well-being: *Modified Caregiver Burden Inventory* (CBI; 5-point Likert scale questions) 24 items comprising five subscales: *Time*, *Physical*, *Social*, *Emotional*, *Developmental*. *Positive Aspects of Caregiving Scale* (PAC; 5-point Likert scale questions) measures the perceptions of the benefits of caregiving (9 items.)

Data Collection and Management

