Data from surveys will be manually entered directly into REDCap, an encrypted online data capture and storage system. REDCap (Research Electronic Data Capture) is a HIPAA-compliant system hosted at the University of Utah Center for Clinical and Translational Science (CCTS). REDCap is a secure, web-based application designed to support data capture for research studies, providing 1) an intuitive interface for validated data entry; 2) audit trails for tracking data manipulation and export procedures; 3) automated export procedures for seamless data downloads to common statistical packages; and 4) procedures for importing data from external sources. Participant questionnaires are delivered in person, de-identified, and entered manually by research staff into REDCap, where it is securely stored and protected. Manually entering data into REDCap reduces incorrect data entry, as the system is built to limit the type of data entered for each question, and allows for checking entry by multiple members of the research team. This enhances security and protects confidentiality of data. Focus groups will be audio recorded, and intervention testing will be video recorded. Audio recordings will be transcribed by a professional transcriptionist and de-identified. Video and audio recordings and transcriptions will be uploaded to a secure shared file on the U of U protected electronic environment. Recordings on digital devices will be deleted once they are backed up to protected servers. These digital recordings are used to examine intervention feasibility. Field notes and journaling from observations will be typed into a password protected and encrypted computer, de-identified, and saved to the UofU protected electronic environment.

Statistical Management & Analysis

The primary goal is to assess feasibility and acceptability of the EnACT intervention within the context of a randomized study, as well as the study protocol. Based on research best-practices guidance from NIH and noted experts, pilot studies—due to their smaller sample sizes and the frequent design adjustments necessary to maximize recruitment, retention, and quality assessment of outcomes—cannot definitively test hypotheses, nor can they provide reliable effect-size estimates. Nevertheless, this pilot will assess whether a subsequent full-scale RCT (NIH Stage III) modeled after this pilot is logistically feasible and acceptable.

Analysis

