Descriptive statistics will be used to describe screening, recruitment, enrollment, retention, completion rates, and satisfaction survey results. Qualitative data will be analyzed based on each construct of feasibility and acceptability. NVivo software will be used to organize qualitative data analysis and document an audit trail. Digital audio recordings will be professionally transcribed. Video and written documentation will be directly imported and analyzed in the software. Data will first be coded using these constructs as a priori codes. Then within each code, pattern coding will be used to group data to facilitate descriptions of the screening, recruitment, and enrollment process. In addition, we will use qualitative data to describe reasons for attrition, engagement, satisfaction with the intervention, and intervention delivery. The PI and RA will meet weekly to analyze data, and monthly with the larger team to resolve conflicts in coding and to group patterns into major themes. The use of both quantitative measures and qualitative observations will allow for a rich, in-depth description of both feasibility and acceptability of this intervention.

Feasibility of Outcome Measures

Seven instruments (demographics, *The Survey of Imagined Interactions*, *Resilience Scale*, *The Revised Caregiving Appraisal Scale*, *Perceived Stress Scale*, *Modified Caregiver Burden Inventory*, and *Positive Aspects of Caregiving Scale*) will be used to assess potential outcomes associated with the theoretical framework for this study. Participants in Stage-1b will take the demographic questionnaire at time one and the other instruments at all 6 timepoints. We will gather data on the duration of these tests, proportion completed, and the burden associated with these measures at each timepoint. This will include documenting retention rates, timepoint completion rates, length of intervention meetings, the amount of time to complete measures, and field notes regarding reactions to taking the battery.

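### The satisfaction survey, the only acceptability measure that yields a figure, is filled in only during sessions, so people who miss sessions or stop attending are under-represented and the figure may overstate acceptability.

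*Combined protocol and SAP*

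**What the plan says.** Statistical Management & Analysis sets the aim: "The primary goal is to assess feasibility and acceptability of the EnACT intervention within the context of a randomized study". The same section says what the result is for: "this pilot will assess whether a subsequent full-scale RCT (NIH Stage III) modeled after this pilot is logistically feasible and acceptable".

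Measures lists three sources: "Acceptability: satisfaction with intervention, audio/video documentation of intervention meetings, post-intervention focus groups". Assessment Schedule fixes when two of them are collected. For satisfaction: "Satisfaction surveys will be gathered at the end of each intervention session as part of the session". For the focus group: "Focus group data will be gathered during the debrief meeting two weeks after intervention meetings are complete". On who comes to that meeting, Time Commitment says only that "participants will be invited to meet together to discuss thoughts about the caregiver training activities".

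The Analysis section gives the quantitative treatment: "Descriptive statistics will be used to describe screening, recruitment, enrollment, retention, completion rates, and satisfaction survey results". It adds that qualitative data will describe why people left, how engaged they were and how satisfied they were. No denominator for satisfaction is stated, and no interval is planned for satisfaction or for any feasibility rate. The 95% intervals mentioned later belong to the regression of the outcome scales.

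**The concern.** A rating taken at the end of a session can come only from people who attended it. Caregivers who miss sessions are the group whose opinion matters most for deciding whether the programme is acceptable, because some of them may be absent for the very reason that they did not like it. If so, average satisfaction among those present rises as the dissatisfied leave, and a programme that loses people can still show a high satisfaction figure.

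At stake is one half of the primary conclusion, and with it the judgement on whether a full-scale trial built on this pilot would be acceptable. With 30 participants, a bare percentage also conveys more certainty than the data hold.

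**Working it through.** The plan states no figure for acceptability, attendance or dropout, so there is nothing of its own to reproduce. The check has two parts.

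**1. Which sources can carry a rating from someone who is absent?**

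| Source | Where described | Reaches people who miss sessions? |
|---|---|---|
| Satisfaction survey | Assessment Schedule | No, for any session missed |
| Audio/video of meetings | Measures | No, it records those present |
| Debrief focus group | Assessment Schedule, Time Commitment | Possibly; participants are invited, but the plan does not say whether those who stopped attending or withdrew are included. It gives themes, not ratings |
| Reasons for attrition (qualitative) | Analysis | Yes in intent, but gives no rating |
| Retention and completion rates | Measures, Analysis | Counts them, but gives no opinion |
| T1 to T6 surveys | Assessment Schedule, Measures | Sent to all, but no instrument asks about satisfaction with EnACT. The Satisfaction subscale of the Revised Caregiving Appraisal Scale is part of an appraisal of caregiving |

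Handling of Missing Data concerns the maximum likelihood models and says nothing specific to absent satisfaction ratings. The survey is repeated at each of three sessions, so a person who attends session 1 and then leaves has rated session 1. What is lost is any rating from people who attend none, and any rating of later sessions or of the whole programme from people who stop.

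**2. How large could the effect be?** All attendance and satisfaction figures below are assumptions, including the reduction of the survey to satisfied or not satisfied. Only N = 30 comes from the plan.

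*Bounds.* Take one overall rating per person, r raters and s satisfied among them. Over all 30 the proportion lies between s/30 (no non-rater satisfied) and (s + 30 − r)/30 (all satisfied).

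- r = 22, s = 20: among raters 20/22 = 91%. Lower bound 20/30 = 67%; upper bound (20 + 8)/30 = 28/30 = 93%.
- r = 24, s = 22: among raters 22/24 = 91.7%. Lower bound 22/30 = 73.3%; upper bound (22 + 6)/30 = 28/30 = 93.3%.

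*Bias.* Overstatement = d × (p1 − p0), where d is the share not rating, p1 satisfaction among raters and p0 satisfaction among non-raters. With p1 = 0.90:

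| d | p0 = 0.30 | p0 = 0.50 | p0 = 0.70 | p0 = 0.90 |
|---|---|---|---|---|
| 0.10 | 6 points | 4 | 2 | 0 |
| 0.20 | 12 | 8 | 4 | 0 |
| 0.30 | 18 | 12 | 6 | 0 |
| 0.40 | 24 | 16 | 8 | 0 |

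The formula gives zero when nobody is absent or when absence is unrelated to satisfaction, and turns slightly negative if p0 exceeds p1.

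*Sampling error.* The exact (Clopper-Pearson) 95% limits for x of n are the 0.025 quantile of Beta(x, n − x + 1) and the 0.975 quantile of Beta(x + 1, n − x).

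- 20/22 satisfied: 70.8% to 98.9%.
- 24/30 retained: Beta(24, 7) and Beta(25, 6) give 61.4% to 92.3%.

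**The case against.** The strongest reply is that acceptability does not rest on this survey alone. The debrief is a separate, paid meeting two weeks after the last session with no stated attendance condition. It asks about barriers, improvements and comparison with other programmes, and reasons for attrition are to be described. Retention, engagement and completion are reported next to satisfaction, so poor attendance would be visible. Descriptive analysis is normal for a Stage 1b pilot, and the plan disclaims definitive testing. All of this stands, and it limits the point to the satisfaction figure.

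Three stronger readings are tempting, and the documents do not support them.

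- *That people who leave never rate anything.* The survey is given at every session, so those who attended at least one full session have been asked about it.
- *That the figure is biased upward.* This is a risk. Caregiving demands are an obvious alternative cause of absence, and the bounds above include values higher than the rater-only figure.
- *That the result cannot come out negative.* Low scores, poor retention or critical focus-group themes can all be reported. What the plan lacks is a figure saying which result would count against a full trial, and leaving that open is a missing detail in a pilot of this kind.

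It is also fair that an all-randomised denominator mixes attendance with opinion. For that reason the bounds should accompany the rater-only figure and not replace it.

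**Conclusion.** The point holds for the satisfaction survey. It is collected from session attenders only, no other instrument asks for a rating of EnACT, and no denominator or interval is stated. If absence is related to dislike, the satisfaction figure may overstate acceptability. The other sources soften this without supplying the missing ratings.

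The size is not derivable from the documents. Under the assumptions shown, 91% among 22 raters is compatible with 67% to 93% over 30, and overstatement runs from 0 to 24 points for 10% to 40% not rating and 30% to 90% satisfaction among them. With near-complete attendance the issue largely disappears. It merits a change because the remedy is cheap and concerns half of the primary goal.

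**What to change.** 1. Add a few overall-satisfaction items and one item on reasons for missing sessions to the existing post-intervention survey: T4 (Week 8) for Group A, whose last session is in Week 6, and T6 (Week 14) for Group B, whose last session is in Week 12. Ask everyone still in the study, whether or not they attended.
2. State that these two surveys go by phone or internet to anyone who does not come in. Time Commitment already provides for this, but Data Collection and Management also speaks of delivery in person, and the debrief falls in the same weeks. If the survey were given only at the debrief, the selection would return.
3. For each session report the numbers randomised, attending and rating.
4. Report satisfaction among raters together with best- and worst-case bounds over all randomised. Withdrawn participants, including those administratively withdrawn after a serious adverse event, will still be missing.
5. Give exact 95% confidence intervals for satisfaction and the main feasibility rates.

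A progression figure is optional, and the sponsor's to choose before results are reviewed. One is workable at this size: purely as an illustration, requiring at least 23 of 30 satisfied would be met with probability 0.044 if the true rate were 60% and 0.76 if it were 80%.

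Cost: 1 to 2 extra minutes on one survey per participant, and a few sentences in the Analysis section.

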Sample Size/Power Analysis: We will recruit 30 dementia caregivers from the community. Participants enrolled will be randomly assigned to the group-based EnACT intervention ($n = 15$) and a waitlist control group ($n = 15$). As an NIH Stage 1b pilot study, the goal is to assess the plausibility of this work in order to guide the next stage of research. Thus, it should not be expected that the sample size will have outstanding power. Constrained longitudinal data analysis will be used on the data set ($N = 30$) to exploit randomization and integrated with the full longitudinal impact data to give greater power than more limited analyses. Simulations conducted in SAS and analyzed under the integrated model yield a respectable power of .70 against the null hypothesis when the hypothesized slope difference corresponds to a medium effect size of .5.

Sites

The intervention will take place at locations associated with our community partners' caregiver support groups, including senior centers, the Division of Aging & Adult Services, and offices of the Utah Chapter of the Alzheimer's Association. This includes online synchronous platforms such as Zoom.

Eligibility

Inclusion Criteria:

Persons providing primary, informal, support to family members with Alzheimer's disease or related dementia (ADRD). These individuals are 18 and older, and the ability to read and speak English.

Exclusion Criteria:

Formal caregivers, persons under the age of 18, and individuals who have English fluency ratings of *none* or *poor* will be excluded.

Recruitment

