Descriptive statistics—including frequency counts, percent distribution, range, mean, median, and standard deviation—were calculated for all variables and timepoints. Descriptive statistics will be reported for the full sample ($n = 30$), and then for the immediate ($n=15$) and wait-list ($n=15$) groups. We will conduct independent samples statistics (chi-square, Fisher's exact test, Student's t test, and Mann–Whitney tests), as appropriate, to statistically compare immediate to wait-list groups for baseline equivalency. We will use generalized linear categorical dose-response models where the effect of intervention over time on the main and secondary outcomes are estimated. Specifically, the regression controls for baseline measures and defines and estimates two separate parameters: D1, natural change at week 8 and D2 the additional impact of the intervention at week 8. The null hypothesis of natural benefit in the waitlist at 8 weeks (D1) is defined as $D1 = 0$. The null hypothesis of no additional benefit of the intervention is $D2=0$ for week 8 (intervention) and week 14 (end of intervention phase in waitlist control). The overall intervention change is defined as the linear combination of $D1+D2$. Importantly, this

framework allows the change in outcomes in the waitlist control during their active intervention phase to contribute to the estimate of D2 which is advantageous for the current smaller sample size. All alphas will be set at 0.05 but the focus will be to examine the direction and magnitude for promising trends to be validated in a future fully powered study. Estimation is done with maximum likelihood and we will report 95% lower and upper confidence intervals.

Handling of Missing Data

Using maximum likelihood estimation, we will use all available data for analysis. This allows us to reduce bias in the estimation. The maximum likelihood estimates given the observed data points are the values most likely to have generated the complete ensemble of observed sample data under the assumed model. Missing data patterns will be examined and imputation if assumption of missing at random is not rejected may be considered in the presence of significant amount of missing data.

Ethical Issues

Ethical Considerations

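### Maximum likelihood with 30 participants and no small-sample correction will tend to make the 95% intervals for D1, D2 and D1+D2 too narrow, by an amount that depends on choices the plan leaves open

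*Combined protocol and SAP*

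**What the plan says.** The Sample Size section fixes 30 participants, 15 per arm, and names constrained longitudinal data analysis. The Assessment Schedule gives six survey points, T1 to T6. Under Feasibility of Outcome Measures the model is described again, as a categorical dose-response model in which "the regression controls for baseline measures and defines and estimates two separate parameters": D1, the natural change at week 8, and D2, the added effect of the intervention. D2 is shared, because the "framework allows the change in outcomes in the waitlist control during their active intervention phase to contribute to the estimate of D2".

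On estimation and inference the same section says "Estimation is done with maximum likelihood and we will report 95% lower and upper confidence intervals" and "All alphas will be set at 0.05 but the focus will be to examine the direction and magnitude for promising trends". Handling of Missing Data repeats the method: "Using maximum likelihood estimation, we will use all available data for analysis". Nowhere do the documents mention REML, a degrees-of-freedom method, another small-sample correction, the form of the within-person covariance, or whether intervals use normal or t quantiles.

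**The concern.** Maximum likelihood estimates variances without allowing for the mean parameters that were fitted, so they are biased downward. Wald intervals built on them also treat the estimated covariance matrix as if it were known. Both effects fade in large samples. With 30 people and up to six correlated measurements each, they need not be negligible.

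The quantitative output of this pilot is a set of effect estimates with their intervals, to be used to pick trends for a larger study. If intervals labelled 95% cover less than that, precision is overstated and somewhat too many outcomes will look promising. Because the covariance structure and reference distribution are not fixed in advance, the actual error rate also depends on choices that could be made after the data are seen.

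**Working it through.** **The plan's own figure.** The documents give no coverage or type I error figure. The nearest is a simulated power of 0.70 for a slope difference of effect size 0.5. It cannot be reproduced, because the within-person correlation and slope variance are not given. A shared-D2 model fitted by ML with z gives power 0.57-0.60 at correlation 0.7 and 0.75 at 0.8 with three visits. With six visits and compound symmetry it gives 0.66 and 0.81. So 0.70 is attainable, and this point does not dispute it.

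**Inputs from the documents.** N = 30, 15 per arm; six visits; ML; alpha 0.05; D2 shared between arms.

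**Assumptions.** Two-sided tests (sidedness is not stated, but lower and upper limits are to be reported); normal outcomes; correlation 0.5 to 0.8; complete data, with 20% dropout as a sensitivity; unstructured or compound-symmetry covariance; z or t(28) reference.

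**Step 1: closed form for a baseline-adjusted regression.** With n people and p mean parameters, ML uses RSS/n instead of RSS/(n-p). The type I error with a z reference is P(|t(n-p)| > 1.96 × sqrt((n-p)/n)).

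- n = 30, p = 3: 1.96 × sqrt(27/30) = 1.859, giving 7.4%.
- n = 30, p = 4: 1.96 × sqrt(26/30) = 1.825, giving 8.0%.
- n = 30, p = 6: 1.96 × sqrt(24/30) = 1.753, giving 9.2%.
- n = 24, p = 3 (20% loss): 1.96 × sqrt(21/24) = 1.833, giving 8.1%.

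With t(28) quantiles the three n = 30 cases give 6.2%, 6.8% and 7.9%. With the unbiased variance but z quantiles they give 6.0%, 6.1% and 6.2%.

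**Step 2: simulation of the constrained longitudinal model under no effect, fitted by ML.** Three visits means weeks 0, 8 and 14. Each cell is the range over the correlations examined (2,000 to 10,000 replicates).

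| Visits, effect tested, fitted covariance | ML with z | ML with t(28) |
|---|---|---|
| 3, shared D2, unstructured | 9.0-9.5% | 7.6-8.1% |
| 3, separate week-8 effect, unstructured | 7.5-8.2% | 6.3-6.9% |
| 6, shared D2, unstructured | 12.4-13.1% | 10.9-11.6% |
| 6, separate week-8 effect, unstructured | 7.6-9.4% | 6.6-8.1% |
| 3 or 6, compound symmetry, correctly specified | 5.5-6.8% | 4.4-6.0% |

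Coverage is 100% minus these figures. With 20% dropout and three visits (1,000 replicates), ML with z gives 8.8-9.3% unstructured and 6.4% with compound symmetry.

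**Step 3: where the excess comes from.** In a separate three-visit unstructured run at correlation 0.6 (8,000 replicates), ML with z gives 8.1%, ML with t(28) 6.6%, and a REML-type covariance with t(28) 5.9%. Of the 8.1 - 5.0 = 3.1 points of excess, 8.1 - 6.6 = 1.5 come from the z reference and 6.6 - 5.9 = 0.7 from ML rather than REML. The remaining 5.9 - 5.0 = 0.9 is left when the estimated covariance is treated as known.

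**Step 4: the remedy, at correlation 0.6.** REML with z leaves 7.2-8.5% (three visits, unstructured) and 9.8-12.0% (six visits, unstructured). REML with Kenward-Roger gives 5.1-5.6% and 6.3-6.7% respectively, and 4.3-5.0% under correct compound symmetry.

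**Precision and limits.** Monte Carlo error is about 0.2-0.6 points for most ML figures. It is about 1 point for the 600-replicate Kenward-Roger runs (six visits, unstructured) and the dropout runs. The simulations tested D2 or the week-8 effect. D1 and D1+D2 were not simulated separately, but they rest on the same variance estimates.

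**The case against.** The strongest reply is that the size is not determined by the text. A reader might infer that the planned intervals cover 90-93% and the tests run at 7-10% as a direct result of using maximum likelihood. The documents do not support that. They name neither a covariance structure nor a z reference, and they describe the model in two ways. Under a correctly specified compound-symmetry model with t(28), ML is close to nominal; under a six-visit unstructured model with a shared D2, it is worse than that range. This part of the reply stands, and the figures must be read as conditional.

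A second reply is that ML is not the main cause. That also stands in part: Step 3 puts the ML-versus-REML share at 0.7 of 3.1 points. It changes the remedy more than the finding, since switching to REML and nothing else would leave most of the excess.

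A third reply is that the trial is exploratory. Statistical Management & Analysis makes feasibility and acceptability the primary goal and disclaims definitive tests and reliable effect sizes. No progression rule hangs on a p-value. This lowers the stakes, but the plan still states null hypotheses for D1 and D2, an alpha of 0.05 and 95% limits. Where estimates with uncertainty are the product, the width of the interval matters.

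**Conclusion.** The concern holds as a conditional one. ML with 30 participants and no small-sample correction tends to give intervals that are too narrow. With a z reference and a suitable covariance structure, type I error is about 5.5% to 13%, so coverage is about 87% to 94.5%. With t(28) it runs from about nominal to 11.6%. These figures assume normal outcomes and correlations of 0.5 to 0.8.

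The direction is not guaranteed if the covariance is wrong. Fitting compound symmetry when correlation decays over time gave 3.0% with three visits and 8.3% with six (ML, z), which reflects misspecification rather than ML alone.

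A reader might go further and conclude that the pilot's estimates are biased or its main aim compromised. Neither follows. The problem lies in the interval widths and tests, not in the point estimates, and the feasibility and acceptability results do not use this model. The change is worth making, but the trial does not stand or fall on it.

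**What to change.** In the estimation sentence, replace maximum likelihood with REML, using Kenward-Roger standard errors and degrees of freedom for every D1, D2 and D1+D2 estimate. Make the matching change under Handling of Missing Data. REML still uses all available data under missing at random, so the rationale given there survives.

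State the covariance structure in advance. If all six visits are modelled, a parsimonious structure is preferable, because Kenward-Roger with an unstructured matrix still gave 6.3-6.7% (about 1 point of simulation error). It should be plausible for these measures: Kenward-Roger does not repair a wrong structure. With compound symmetry fitted to decaying correlations it gave 6.7% with six visits and 1.7% with three.

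The cost is a software option, two or three sentences and wider intervals. In the regression case of Step 1, the correct t quantile against the uncorrected multiplier gives 2.052/1.859 = 1.10 with three mean parameters and 2.064/1.753 = 1.18 with six, so intervals 10% to 18% wider. That extra width is uncertainty the planned intervals would have left out.
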